#### 1 PROTOCOL SYNOPSIS

**PROTOCOL TITLE:** A Phase 2 Study of PF-04449913 For the Treatment of Acute Myeloid Leukemia Patients with High Risk of Post-Allogeneic Stem Cell Transplantation Relapse

**INDICATION:** Post allogeneic stem cell transplantation for acute myeloid leukemia patients with high risk of relapse

#### STUDY PHASE: 2

**BACKGROUND AND RATIONALE:** Disease relapse is the most common cause of death after allogeneic stem cell transplantation for acute myeloid leukemia. Patients at high risk for relapse may benefit from a novel, biologically rational therapeutic intervention to prevent this outcome. PF-04449913 is a small molecule inhibitor of the hedgehog (Hh) pathway that inhibits the protein Smoothened (SMO). Aberrant Hh signaling may contribute to the survival and expansion of the leukemia stem cell, and inhibiting the Hh pathway can eliminate these cells. Therefore, targeting Hh may be a logical intervention in the post-transplantation setting for those with high risk of relapse. We propose a phase 2 study of PF-04449913 in patients with acute myeloid leukemia who have received an allogeneic stem cell transplantation and are at high risk of relapse.

#### STUDY OBJECTIVES:

#### Primary:

• Determine whether PF-04449913 can prevent relapse in high risk acute myeloid leukemia patients who receive an allogeneic stem cell transplantation

#### Secondary:

- Determine the toxicity profile of PF-04449913 in this population
- Determine the impact of this intervention on overall survival (OS)

#### STUDY DESIGN:

This is an open label, phase 2 study employing PF-04449913 in acute myeloid leukemia patients who received an allogeneic stem cell transplantation and are at high risk of relapse. Patients will receive consecutive 28-day cycles of PF-04449913 at 100 mg/day, beginning on post-transplantation day 28-50, after their routine post-transplant bone marrow biopsy. Treatment will continue for up to one year or until they experience toxicity or disease relapse. 50 patients will be required for a 90% power to detect a 20% difference in one-year relapse free survival.

#### STUDY ENDPOINTS

#### Primary:

• One year relapse-free survival

#### Secondary:

- Remission duration
- Incidence and severity of adverse events
- OS (one year)

STUDY DURATION: 5-7 years	TOTAL SAMPLE SIZE: 50

## 2 SCHEDULE OF STUDY ASSESSMENTS\*

		PF- 04449913	Hx/PE	Hematology	Chemistry	Screening Labs & Procedures	12-Lead EKG	MRD	BM Bx
Screening†			Х	Х	Х	Х	Х		
	Days 1-28	Х							
Cycle 1	Day 1		X	X¶	X¶		Х		
	Day 15		Х	Х	Х		Х		
	Day 28 ‡		Х	Х	Х				
Cycles 2 - 12	Days 1-28	Х							
	Day 1 ‡		Х	Х	Х		X †*		
Initiation of New Azole Antifungal Medication							X ¶*		
Post-transplant day 80 +/- 10 days								Х	Х
Post-transplant day 175 +/- 15								Х	Х
Post-transplant day 365 +/- 30								Х	Х

#### **DEFINITIONS:**

**Hx/PE:** Complete or interim medical history, including ECOG performance status, adverse event monitoring and concomitant medications review; complete or focused physical examination. Drug compliance assessment will occur with each cycle's day 1, beginning with cycle 2.

Hematology: Complete blood count (includes hemoglobin, hematocrit, platelet count and total white blood cell count with differential)

**Chemistry:** Complete metabolic profile, including Na, K, calcium, CO2, BUN, creatinine, glucose, magnesium, phosphorous, protein, albumin, AST, ALT, alkaline phosphatase and total bilirubin

**Screening labs & procedures:** Prothrombin time (PT) and/or international normalized ration (INR), partial thromboplastin time (PTT); serum/urine pregnancy test for women of childbearing potential only must be performed within 72 hours of treatment initiation.

12-lead EKG: To be performed with QTc interval calculated by Fridericia's correction factor if indicated.

MRD: Minimal residual disease, as detected by multidimensional flow cytometry (see Section 5.12.5.6)

BM Bx: Unilateral core and aspirate samples, to be sent for morphological assessment, cytogenetics, flow cytometry and molecular testing

#### FOOTNOTES

\*Variations of ±5 days of scheduled visits are permitted; unscheduled visits can occur at any time during the study. The date of the unscheduled visit and any data generated must be recorded on the appropriate case report form, and source documents for these visits must also be maintained.

†Includes review of exclusion/inclusion criteria and informed consent.

If screening and day 1 are  $\leq$  7 days apart, the Hx/PE, CMP and CBC performed at enrollment do not need to be repeated on day 1.

‡Day 28 visit and labs may be same as day 1 visit and labs of the subsequent cycle

\*\*\*Perform 1-4 hours after first dose (at Cmax)

+\* Perform 1-4 hours after first dose (at Cmax) for cycle 2, day 1 only; not necessary to routinely repeat on day 1 of each cycle unless clinically indicated

®Perform 2-5 days after initiation of new azole antifungal medication

## 3 INTRODUCTION

Hematopoietic stem cell transplantation (HSCT) is the only therapy with curative potential for high risk patients with acute myeloid leukemia (AML) However, disease relapse remains the main cause of treatment failure and death after HSCT, suggesting that even highly ablative therapies and the generation of immunological graft versus leukemia responses are very often unable to target the leukemia stem cell population and achieve the requisite cure. At relapse, salvage maneuvers such as secondary transplantations or donor lymphocyte infusions are highly toxic and seldom effective, highlighting the need for tolerable therapies in this population.

Predicting imminent relapse in the post-transplant setting is becoming increasingly sophisticated. In post-transplant patients, flow-cytometry based minimal residual disease (MRD) detection for AML has been shown to be highly predictive of relapse and overall survival (OS). Molecular analyses of leukemia fusion genes can also allow for disease monitoring in select patients, and persistence of a cytogenetic abnormality at the time of transplantation is a poor predictor for relapse and OS after a myeloablative HSCT.

Developing clinical trials for AML post-allogeneic HSCT patients with imminent or high-risk of relapse is an area of active interest that warrants further exploration using novel therapies.

# 3.1 Background and Rationale

The Hedgehog (Hh) signaling pathway regulates essential elements of embryonic development, homeostasis and tissue regeneration and development. It is important in a broad range of cancers, including basal cell carcinoma, bladder, colorectal, lung, pancreas, prostate and stomach. Hh signaling is activated by binding of one of three Hh ligands, Sonic Hedgehog (Shh), Indian Hedgehog (Ihh), or Desert Hedgehog (Dhh) to their receptor, Patched (Ptch). Binding of Hh ligand to Ptch alleviates repression of a second transmembrane protein, Smoothened (SMO), allowing SMO to transduce the signal to the cytoplasm resulting in activation of Gli family zinc finger transcription factors (Gli1, Gli2 and Gli3). Gli translocates into the nucleus and activates transcription of target genes, causing proliferation.

Activation of the Hh pathway can occur by two mechanisms. First, mutations in Ptch or SMO genes result in constitutive activation of the pathway and upregulation of Gli. Mutations in Hh signaling members have been reported in basal cell carcinoma, medulloblastoma, and rhabdomyosarcoma. A direct link between mutation driven aberrant Hh signaling and human tumorgenesis is found in Gorlin Syndrome, characterized by the development of multiple basal cell carcinomas, and are predisposed to medulloblastoma and rhabdomyosarcoma. These patients have a germline inactivating mutation in the repressor Ptch that results in constitutively active SMO and upregulation of Hh target genes. The link between mutations in Ptch and basal cell carcinoma was also reported in a majority of sporadic basal cell carcinoma tumors, 18,19 and a significant number of sporadic medulloblastomas can also be attributed to inactivating mutations in *Ptch*. To test these findings, a genetically engineered mouse model of medulloblastoma was developed by genomic deletion of a Ptch allele; the heterozygous Ptch deletion mutation, coupled with a deletion of p53, resulted in posterior fossa tumors with active Hh pathway signaling and upregulated expression of Gli target genes.

## Hypothesis

PF-04449913 will be well-tolerated and effective therapy for acute myeloid leukemia patients who have received HSCT and have high risk of disease relapse. We aim to test this hypothesis with this phase 2 clinical study.

## 3.2 PF-04449913

Cyclopamine, isolated from the corn lily plant, interacts with and inhibits SMO. PF-04449913 was synthesized to improve the hepatic clearance, decrease the lipophilicity and increase the solubility of cyclopamine. PF-04449913 is a potent and selective inhibitor of Hedgehog (Hh) signaling *in vitro* and has demonstrated significant antitumor efficacy *in vivo*.

## Chemical Structure of PF-04449913

Molecular weight: 374.439 daltons

Chemical name: 1-((2R,4R)-2-(1H-benzo[d]imidazol-2-yl)-1methylpiperidin-4-yl)-3-(4-cyanophenyl)urea dihydrochloride monohydrate

Molecular Formula: C21H26Cl2N6O2 (dihydrochloride monohydrate)

6

Physical description: White to pale-colored powder

Bioavailability: Oral

## **Pre-Clinical Data**

#### Pharmacokinetics/Pharmacodynamics and Metabolism

Preclinical pharmacokinetic (PK) / pharmacodynamics (PD) modeling suggests a target human dose of 15 mg/day is projected to yield at least 50% of tumor Gli1 mRNA inhibition from baseline levels. A 15 mg dose is projected to result in a Cmin of 62 ng/mL total (5.6 ng/mL free) and a Cave of 79 ng/mL total (7.2 ng/mL free).

Absolute oral bioavailability of PF-04449913 following single dose oral administration was 33% in rats and 68% in dogs. Plasma protein binding of PF-04449913 in mouse, rat, dog, and human plasma ranged from 85% to 93%. A volume of distribution at steady state (Vss) of 4.78 and 4.21 L/kg was observed in rats and dogs, respectively.

PF-04449913 was evaluated in rat and dog repeat-dose toxicity studies up to 1 month in duration. PF-04449913 was well tolerated up to 50 mg/kg/day in the rat and 5 mg/kg/day in the dog. In both the rat and the dog, a greater than proportional increase in exposure occurred with increasing dose. In the rat study, the increase in mean AUC(0-24) values were approximately 175-fold and 232-fold greater than the dose (50-fold) range evaluated for Day 1 and Day 29, respectively. In the 1-month dog toxicity study, the mean AUC(0-24) values were approximately 165-fold (male) and 360-fold (female) greater than the dose (30-fold) range evaluated on Day 1.

*In vitro* metabolism of PF-04449913 was consistent across preclinical species and humans. All metabolites observed in human *in vitro* incubations were present in one or more of the evaluated preclinical species. PF-04449913 appeared to be metabolized to several oxidative metabolites. Preliminary assessment using individual recombinant P450 enzymes suggests that CYP3A4 plays a major role in mediating the metabolism of PF-04449913 *in vitro*.

PF-04449913 was evaluated *in vitro* in human liver microsomes for the potential to inhibit CYP enzymes. Preliminary results show that PF-04449913 does not inhibit CYP1A2, CYP2C8, CYP2C9, CYP2C19, CYP2D6, or CYP3A4 at concentrations up to 30  $\mu$ M (11.2  $\Box$ g/mL).

In cryopreserved human hepatocytes, PF-04449913 does not induce CYP1A2 or CYP3A4 mRNA levels and enzyme activities at unbound concentrations up to 100  $\Box$ M (37.4  $\Box$ g/mL). Considering the human pharmacokinetics observed to date, PF-04449913 is not expected to

reduce plasma concentrations of co-administered CYP1A2 or CYP3A4 substrates *in vivo*.

#### **Toxicity**

Deaths and/or moribund euthanasia occurred in the 7-day and 10day rat, and 1-month dog studies at 250, 500 or 30/15 mg/kg/day, respectively. Cause of death/morbidity in both species was attributed to kidney toxicity. The target organ in the rat 1-month toxicity study included kidney (tubular degeneration/necrosis, cytomegaly, inflammation, regeneration) and bone (decreased/disorganized chondrocytes in epiphysis); the no observed adverse effect level (NOAEL) was 10 mg/kg/day (a 5× safety margin over the projected human Cave at steady state). The kidney changes showed some signs of reversibility but did not entirely reverse, while the bone changes persisted.

The target organ in the 1-month toxicity study in the dog was limited to the kidney (tubular necrosis, granular/mineralized casts, dilated tubules); NOAEL was 1 mg/kg/day which is <1× the projected human Cave at steady state. Mild changes in the kidney were observed at 5 mg/kg/day which are 11× the projected human Cave at steady state. The kidney changes in the dog were completely reversed in males and partially reversed in females after a 6-week reversal period. In the acute central nervous system (CNS) and respiratory studies in the rat, no effects were observed at the high dose of 50 mg/kg (55× above the projected human efficacious Cmin at steady state). Increases in QT, QTc75 were noted after single doses of D5 mg/kg to dogs which is 
49× above the projected human efficacious Cmax at steady state. PF-04449913 was negative in the definitive in vitro bacterial mutagenicity assay, human lymphocyte assay and the in vivo rat micronucleus. The molar extinction coefficient for PF-04449913 at 290 nm is 9622 L/mol/cm; therefore, PF-04449913 has the potential to be phototoxic.

To evaluate potential effects on the central nervous system, PF-04449913 was administered as a single dose to male rats, and motor activity, behavioral changes, coordination, sensory/motor reflex responses, and body temperature were evaluated. There were no effects in either the functional observational battery or locomotor activity assessment at doses up to 50 mg/kg. The maximum plasma concentration at 50 mg/kg free group mean Cmax of 617 ng/mL from the 1-month rat is 72-fold above the projected human free efficacious Cmax concentration of 8.6 ng/mL. To evaluate the potential effect on the cardiovascular system, PF-04449913 was evaluated for its effect on binding to the hERG potassium channel stably expressed in human embryonic kidney (HEK-293) cells

(PF4449913/ESD/1108/HERG). The hERG IC50 for PF-04449913 was 3.1 DM which is 163-fold above the projected free human efficacious (Cave) drug concentration of 19 nM and 135-fold above the projected human free efficacious Cmax (23 nM). To further investigate QT prolongation and any hemodynamic changes due to inhibition of several receptors outlined in the secondary pharmacodynamics section, PF-04449913 was administered by oral gavage to conscious telemeterized dogs at dose levels of 1, 5 and 30 mg/kg. At dose levels of 5 and 30 mg/kg, PF-04449913 produced a statistically significant and dose dependent increase in QT and QTc75 which was apparent up to at least 14 hours post-dosing. The maximum observed QTc75 prolongation was 6 and 24 msec at 5 and 30 mg/kg, respectively. Increases in heart rate (10 beats per minute) occurred in the 30 mg/kg treated dogs which were coincident with episodes of emesis and are most likely related to the latter effect. There was also a small increase (3 msec) in the QRS interval after the 30 mg/kg treatment and this was apparent up to 14 hours postdosing. This latter effect is consistent with the weak sodium channel inhibition observed in a functional patch clamp study (see the secondary pharmacodynamics section). There were no statistical or remarkable changes in dogs treated with 1 mg/kg PF-04449913. At 5 mg/kg, the peak free plasma concentration in male and female dogs was 517 ng/mL and 420 ng/mL, respectively (from the 1-month dog). This represents a 49 to 60-fold margin above the projected free Cmax (8.6 ng/mL) at a human efficacious dose of 15 mg. PF-04449913 was administered as a single dose to male rats to assess potential effects on the respiratory system. PF-04449913 had no effect on respiratory rate, tidal volume or minute volume at doses up to 50 mg/kg. The maximum plasma concentration at 50 mg/kg (free mean Cmax of 617 ng/mL from the 1-month rat is 86-fold above the projected human (Cave) drug concentration of 7.2 ng/mL and 72-fold above the projected human free efficacious Cmax (8.6 ng/mL).

## **Clinical Data**

See current PF-04449913 Investigator's Brochure – released by Pfizer (manufacturer).

Several clinical studies have been initiated to determine the safety, efficacy, pharmacodynamics and pharmacokinetics of PF-04449913 in patients with hematologic malignancies and advanced/metastatic solid tumors. Study B1371001 was a first-in-patient phase 1 trial with a 3+3 dose escalation design in patients with refractory, resistant or intolerant select hematologic malignancies. Patients received single

9

agent PF-04449913 orally once daily (QD) continuously in 28 day cycles. Eight dose levels were evaluated as of September 2011, ranging from 5 mg/d to 270 mg/d. Study B1371002 had a similar 3+3 dose escalation design in patients with select advanced/metastatic solid tumors. The starting dose of PF-04449913 in this study was 80 mg/d and additional dose levels of 160 mg/d and 320 mg/d have been completed to date. Protocol B1371003, a Phase 1b/2 study to evaluate the safety and efficacy of PF-04449913 in combination with various chemotherapy regimens in patients with AML and high-risk MDS, is ongoing.

## Pharmacokinetics/Pharmacodynamics and Metabolism

Preliminary PK data indicate that PF-04449913 is rapidly absorbed following oral dosing with a median Tmax of ~1- 2 hr after single and multiple dose administration. Following attainment of Cmax, PF-04449913 plasma concentrations showed a bi-exponential decline and were eliminated relatively slowly with a mean terminal half-life (estimated from a single dose) ranging from 17.3 to 34.9 hours. Following repeated daily dosing, PF-04449913 steady state was achieved by Day 8 and showed a drug accumulation of ~ 1.5 fold, which is consistent with the estimated half-life. In general, low to moderate inter-individual variability were observed in Cmax and AUC values following single and multiple dose administration, though higher variability was observed at the 180 and 270 mg dose levels.

Hepatic metabolism is predicted to be the major clearance pathway for PF-04449913 in humans. In vitro metabolism of PF-04449913 was consistent across preclinical species and humans. PF-04449913 appeared to be metabolized to several oxidative metabolites. Preliminary assessment using individual recombinant P450 enzymes suggests that CYP3A4 plays a major role in mediating the metabolism of PF-04449913. All metabolites observed in human in vitro incubations were present in one or more of the evaluated preclinical species. In vitro, PF-04449913 did not inhibit CYP1A2, CYP2C8, CYP2C9, CYP2C19, CYP2D6, or CYP3A4 at concentrations up to 30  $\mu$ M. Based on in vitro and in vivo evaluations of PF-04449913, systemic plasma clearance, volume of distribution at steady state, elimination half-life and oral bioavailability in humans are projected to be 1.03 mL/min/kg, 2.7 L/kg, 30 hours and 55%, respectively.

Preliminary data indicates that renal excretion plays a minor role in PF-04449913 elimination, with 4% to 19% (n = 15) of the total

administered dose excreted unchanged in urine. The renal clearance ranged from 0.35 L/hr to 3.4 L/hr.

When 200 mg PF-04449913 was combined with ketoconazole, a strong inhibitor of CYP3A4, in healthy volunteers, there was evidence for a drug-drug interaction resulting in increased exposure (Cmax and AUC) of PF-04449913, potentially to the 400-600 mg range observed to result in grade 3 QTc prolongations in study B1371001.

Study B1371010, a healthy volunteer study investigating the effects of a high fat, high calorie meal on the PK of a single dose of PF-04449913, indicated that food resulted in a 12.7% decrease in AUC and a 34.1% decrease in Cmax for PF-04449913.

#### Toxicity

Preliminary results from a phase 1 study in patients with hematological malignancies revealed grade 3 toxicities of hemorrhagic gastritis, hypoxia and pleural effusions. All other adverse events (AEs) were less than grade 3, and included dysguesia (16%), alopecia (6%), arthralgia (6%), decreased appetite (6%), nausea (6%) and vomiting (6%).32 Roughly 50% of patients had at least a grade 1 AE. This study and others are ongoing.

## Recommended Dose

Due to the potential interaction between azoles and PF-04449913, 100 mg of PF-04449913 has been selected as the recommended dose in the ongoing protocol B1371003.

## 4 STUDY OBJECTIVES

## 4.1 Primary Objective

 Determine whether PF-04449913 can prevent relapse in high risk acute myeloid leukemia patients who receive an allogeneic stem cell transplantation

## 4.2 Secondary Objectives

- Determine the toxicity profile of PF-04449913 in this population
- Determine the impact of this intervention on overall survival (OS)

## 5 INVESTIGATIONAL PLAN

## 5.1 Overall Study Design

This is an open-label, phase 2 study of PF-04449913 administered to acute myeloid leukemia patients after allogeneic stem cell transplantation who have a high risk of disease relapse.

## 5.1.1 Dosing Schema

Enrolled patients will receive 100 mg PO daily of PF-04449913 continuously dosed for 28-day cycles. Patients will begin treatment no sooner than post-transplant day 28 and no later than post-transplant day 50, after their routine bone marrow biopsy is performed. Treatment cycles can continue for one year after initiation of study drug in the absence of the parameters listed in Section 5.10.1: Stopping Rules.

## 5.1.2 Continuation and Interruptions

Each treatment cycle will be initiated at the full 100 mg dose, provided patients have no evidence of disease relapse, excessive toxicity, or laboratory values outside of the following parameters:

- Either creatinine >1.5 x institutional upper limit of normal (ULN) or creatinine clearance <60 mL/min as calculated by institution's standard formula
- Total bilirubin > 2 x ULN (unless documented Gilbert's syndrome)
- AST and ALT > 5 x institutional ULN
- Absolute neutrophil count (ANC) < 1000/mm^3
- Platelet count <25,000/mm^3

Patients who experience toxicity may be eligible for dose deescalation; please see Section 5.13.1 for Definition of Adverse Events and Section 5.10.2.2: Dose Delays and De-Escalation.

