# 5.7 Laboratory Criteria for Initiation of Treatment Cycles

Before any treatment cycle after cycle 1 may be administered, blood samples collected within 72 hours of the first dose of each cycle must meet the following criteria:

- Either creatinine ≤ 1.5 x ULN or creatinine clearance ≥ 60 mL/min as calculated by institution's standard formula
- Total bilirubin ≤ 2 x institutional ULN (unless documented Gilbert's syndrome)
- AST and ALT  $\leq$  5 x institutional ULN
- ANC > 1000/mm^3
- Platelets >25,000/m^3

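### Sections 5.1.2 and 5.7 apply opposite either/or logic to the renal values at cycle start, and the Section 5.10.2.2 text and table differ on whether the original dose is available after grade 4 toxicity

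*Combined protocol and SAP*

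**What the plan says.** **Cycle start.** Section 5.1.2 opens with "Each treatment cycle will be initiated at the full 100 mg dose", on condition that there is no relapse, no excessive toxicity and no "laboratory values outside of the following parameters". The list that follows consists of abnormal values. Its renal item is "Either creatinine >1.5 x institutional upper limit of normal (ULN) or creatinine clearance <60 mL/min". The others are bilirubin above 2 x ULN, AST and ALT above 5 x ULN, "Absolute neutrophil count (ANC) < 1000/mm" and "Platelet count <25,000/mm" (units per cubic millimetre).

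Section 5.7 sets criteria that must be met "Before any treatment cycle after cycle 1 may be administered". Its renal item is "Either creatinine ≤ 1.5 x ULN or creatinine clearance ≥ 60 mL/min as calculated by institution's standard formula". It also requires bilirubin at or below 2 x ULN, AST and ALT at or below 5 x ULN, ANC above 1000, and "Platelets >25,000/m" (the unit prints differently from 5.1.2; nothing here rests on that).

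**Restart after grade 4 toxicity.** The Section 5.10.2.2 text lets the investigator choose the original dose or a 50% reduction, both for non-hematological events of grade 3 or higher and for grade 4 hematological toxicity. The grade 4 column of the toxicity table in the same section offers a 50% reduction or discontinuation. The grade 3 column does offer the same dose level. The text labels the table as guidance, but the line introducing it presents it as how other toxicities will be handled. The second-episode sentence that follows the grade 4 hematological rule names a non-hematological event.

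**The concern.** These passages decide whether a cycle starts at full dose when a laboratory value is abnormal, and whether the original dose may be resumed after a grade 4 event. Two sites could each follow the protocol and treat the same patient differently.

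The renal item matters most. The preclinical toxicity part of Section 3.2 names the kidney as a target organ in both the rat and the dog. A stable patient with one renal value out of range would meet 5.7 and fail 5.1.2 at every cycle. If a site handled the failure as a treatment delay, Section 5.10.2.2 would end that patient's participation after 28 days. A site working from 5.7 would continue treatment.

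**Working it through.** No figure in the plan is to be reproduced. The check is on the logic of the rules.

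**1. Renal rule.** Inputs: the limits 1.5 x ULN (creatinine) and 60 mL/min (clearance), the same in 5.1.2 and 5.7. Section 5.1.2 is read as a list of values that bar a full-dose start, because its items are abnormal values.

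- Let A = creatinine > 1.5 x ULN and B = clearance < 60.
- 5.1.2 permits when not (A or B), that is, when *both* values are in range.
- 5.7 is met when (not A) or (not B), that is, when *at least one* value is in range.

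The inequalities were reversed between the sections but the either/or was kept, so one rule is not the complement of the other. They differ exactly when one of A and B is true.

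| Creatinine (x ULN) | Clearance (mL/min) | 5.1.2 permits full dose | 5.7 met |
|---|---|---|---|
| 1.2 | 80 | yes | yes |
| 1.5 | 60 | yes | yes |
| 1.2 | 50 | no | yes |
| 1.8 | 80 | no | yes |
| 1.8 | 50 | no | no |

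On the full grid of creatinine 1.2, 1.5, 1.8 by clearance 50, 60, 80, the rules differ in 4 of 9 cells (1.2/50, 1.5/50, 1.8/60, 1.8/80). In each, exactly one value is out of range. The count confirms the logic; it depends on the grid chosen and says nothing about how many patients are affected.

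**2. Other laboratory items (minor).**

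- AST/ALT: read literally, 5.1.2 bars only when both exceed 5 x ULN, while 5.7 needs both at or below 5. At 6 and 4 x ULN, 5.1.2 does not bar and 5.7 is not met.
- ANC exactly 1000, or platelets exactly 25,000: 5.1.2 does not bar and 5.7 is not met. At 999 or 1001, and at 24,999 or 25,001, the sections agree.
- Bilirubin: the sections agree.

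The direction is therefore mixed: 5.1.2 is the stricter on renal values and 5.7 on these items.

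**3. Is the case handled elsewhere?** For a patient who meets 5.7 but fails 5.1.2:

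- Section 5.5.2 fixes the cycle at 28 days whatever doses are missed.
- Section 5.10.2.2 does not extend cycles, and its general holds are triggered by the grade and relatedness of an adverse event, not by these laboratory limits.
- Section 5.13.1.1 says when an abnormal value is recorded as an adverse event, including when treatment is interrupted.

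None states the action or dose for this patient.

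**4. Grade 4 restart.** Excluded are QTcF prolongation and myalgia/arthralgia, which have their own rules, and nausea, vomiting or diarrhea, which the table qualifies. For a first event at 100 mg, with 50% x 100 = 50 mg:

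- Text: {100 mg, 50 mg, stop}. Stopping is included because the text is permissive and Section 5.10.1.1 allows termination.
- Table, grade 4 column: {50 mg, stop}.

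The sets differ only in whether 100 mg is available.

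**5. Second episode.** As printed, the text gives a further reduction for non-hematological events twice and does not name one for hematological events. The table's grade 4 column covers both classes.

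**The case against.** The strongest reply is that the two lists do different jobs: 5.1.2 conditions starting at 100 mg, and 5.7 conditions giving a cycle at all. On that reading, passing one and failing the other is not a strict contradiction. This is fair, but it turns the conflict into a gap: the patient may have a cycle, may not have it at full dose, and no action is stated.

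A second reply is that 5.1.2 is loosely worded. Its lead-in speaks of values outside a list that itself consists of abnormal values, so it has to be repaired before it can be applied, and it could have been meant as the simple negation of 5.7. The shared limits make that plausible. It shows that the intent can be guessed, not that it is stated. It also means that the AST/ALT difference, which needs a literal reading of one word, and the single-point ANC and platelet differences carry little weight.

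A third is that the table is only guidance, so the text governs. That would settle the grade 4 question if the table were not then introduced as the way other toxicities will be handled. The documents do not settle its status.

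A fourth is that the practical reach is limited. Section 5.10.3 provides for one protocol version and monthly calls covering dose modifications. Section 5.11 treats a drug-related SAE as study completion, and Section 5.10.1.1 permits termination for related or possibly related SAEs, so fewer patients reach a grade 4 restart. This stands as a limit on size. The calls may expose a difference in practice but do not say which wording applies.

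**Conclusion.** The protocol is wrong as written, as an internal inconsistency in two places. For cycles after cycle 1, Sections 5.1.2 and 5.7 diverge whenever exactly one renal value is out of range; if they are read as governing different things, the resulting case is not clearly provided for. For the grade 4 toxicities within scope, the 5.10.2.2 text and table differ on whether the original dose is available. The remaining slips (the 5.1.2 lead-in, AST/ALT, the exact ANC and platelet boundaries, the second-episode sentence) are minor but should be cleared at the same time.

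The renal conclusion assumes that 5.1.2 is a list of values that bar a full-dose start. The 28-day consequence assumes that a site treats a failed 5.1.2 check as a delay.

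A reader might infer more than the documents support:

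- *That sites are already treating patients differently, or that a known share of patients is affected.* Nothing shows this, and no frequency can be derived.
- *That every eligible patient with one renal value out of range is barred at the first dose.* The eligibility criteria in Section 5.3.1 do use the permissive renal form, but they serve another purpose, and the inference rests on the word "each" in 5.1.2 covering cycle 1. It shows only that the scope needs stating.
- *That the primary result is compromised.* No effect on sample size, analysis or the study stopping rule is claimed.

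**What to change.** - Reconcile Sections 5.1.2 and 5.7 into one cycle-start laboratory list covering renal, bilirubin, AST/ALT, ANC and platelet values, and have the other section refer to it. Word the lead-in so that it matches the direction of the list.
- State the scope of the list, including whether it applies to cycle 1, and what happens to a cycle when the list is not met.
- Reconcile the Section 5.10.2.2 text, including the second-episode sentence, with the table's grade 4 column, and state whether the table is binding or guidance.

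The investigators decide which version stands; no dose or clinical rule is proposed here. The cost is a clarifying amendment with IRB approval and site notification. Whichever version is kept may change who is dosed, and at what dose, at any site that followed the other, so the choice should be made explicitly.
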